1. GLOSSARY OF ABBREVIATIONS & TERMS

Abbreviation	Description (using lay language)
ECEC	Early Childhood Education Centre
WSLHD	Western Sydney Local Health District
The Training	Modified Learning Language and Loving it™ Program (modification approved by the Hanen Centre®)
SP	Speech Pathologist
Educator	Early Childhood Educator

3. FUNDING AND RESOURCES

3.1 SOURCE/S OF FUNDING

This study is supported, in part, by funding received from the Paediatric Innovation Fund from NSW Health awarded to [name], [name], [name], [name], [name], [name], [name], & [name] (2019-2021). Speech Pathologists involved in the project are employed by Western Sydney Local Health District and The University of Sydney.

All Speech Pathologists delivering the modified version of the Learning Language and Loving It™ program were trained by the Hanen Centre®. This training was paid for by a ClubGRANTS grant from Dooleys Lidcombe Catholic Club (2018) and the Paediatric Innovation Fund grant (listed above). All trained Hanen-certified Speech Pathologists pay an annual fee to the Hanen Centre® in order to maintain certification. Despite this financial relationship, the Hanen Centre® has no oversight over the current research study.

4. INTRODUCTION/BACKGROUND INFORMATION

4.1 LAY SUMMARY

This project will investigate the impact of a professional development training program, (herein called the Training) for early childhood educators that has a focus on improving their communication interactions with children in their care. The Training is a modified version of Learning Language and Loving It™ developed by the Hanen Centre®. It was modified by the current research team to suit the needs of the local community. The modification has been approved by the Hanen Centre®. Previous research by the current team established that educators reported increased confidence using trained interaction strategies following the Training. The current study will evaluate the direct change in child and educator language use during communication interactions before and after the Training. We hypothesise that participation in the Training leads to positive child and educator communication outcomes including an increase in the number of interaction skills used by educators following Training, and the length of utterances and complexity of words used by children during these interactions.

Eligible educators and children will be paired by centre of attendance and language background. Children will be aged 24-42 months and have typically-developing communication skills. Twenty-four educator-child pairs will be recruited in two groups: Group A and Group B. Each group of educators will receive the 8-week Training in two separate stages; Group A in Stage 1 and Group B in Stage 2. This will allow for control and follow-up comparisons to be completed (see Figure 1).

Demographic information will be collected from educator and child participants before any training commences. In addition, 15-minute educator-child interactions will be video recorded at four time-points within their early childhood education centre (ECEC). Measures will examine the extent to which educators use target interaction strategies and the way children use language in these interactions. This project will help to address a critical gap in knowledge about whether this modification of the Learning Language and Loving it™ Program has a direct impact on children's communication outcomes.

4.2 INTRODUCTION

There is considerable evidence to suggest that professional development with early childhood educators can have a positive impact on children's communication skills (Markussen-Brown et al., 2017; [name] et al., in preparation). It is understood from previous research that when educators are responsive communicators, the language development of young children is supported by the quality of their interactions (Girolametto, Weitzman & Greenberg, 2006). However, previous research has not considered the effectiveness of professional development training for educators in culturally- and linguistically diverse communities. Further, the direct impacts of the current local adaptation of the Training on child and educator interaction behaviour have not been measured.

The current project is Phase 3 of a study entitled Growing Little Language Learners; Phase 1 and 2 were completed in 2020. In Phase 1, a locally-developed adaptation of an established Training was modified in consultation with a community reference group. In Phase 2, the Training was implemented with 36 Educators in the local community; 71% of educators were multilingual with 25 different languages spoken amongst the group. The current project (Phase 3) will allow us to examine the impact of this integrated model of care on improving the communication outcomes of children.

The current project will be conducted across a 20-month period, commencing in mid-2021. There will be five time points and two stages of educator Training. Participating educators will only complete the Training in one of the two stages.

The study will investigate whether children and their educators change their communication behaviours following the Training and whether the amount of change during the training stage is commensurate with change during the stage where no training is received. We hypothesise that there will be a greater magnitude of communication behaviour change during a period of training (as opposed to a period of time when no training is provided).

Through this investigation, we will determine whether new models of care being implemented by Western Sydney Local Health District (WSLHD) are initiating the expected, positive change in the quality of early childhood communication environments in the local area. The outcomes of this study will support decision making regarding the effectiveness of the Training and therefore the value of future implementation of the Training across communities.

4.3 BACKGROUND INFORMATION

Most children aged 2-3 years old in Australia attend formal or informal childcare with as many as 71% of both age groups reported to attend child care (Australian Bureau of Statistics, 2017). Despite attending childcare, many children in Western Sydney are vulnerable to communication difficulties and health inequities due to cultural and linguistic diversity, socioeconomic vulnerabilities, and access to quality communication environments in their early education centre. A recent review on the state of ECEC care in Cumberland City Council area found that the quality of care in this local government area is lower than the state average, with just 20% of centres rated as exceeding the National Quality Standard, compared to 32% of centres across Australia (Cred Consulting, 2019). Traditional models of care are unable to meet the needs of vulnerable communities as long waiting lists and limited services threaten the wellbeing of children at greatest risk of long-term communication, social, and academic disadvantage. Previous research suggests that high quality child care environments positively impact the language development of children from these low-income backgrounds (McCartney, Dearing & Taylor, 2003).

Child and Family speech pathologists of WSLHD have established a new model of integrated care that provides an evidence-based professional development training to early childhood educators in the local community. This Training – Learning Language and Loving It™ (Hanan Centre®, locally modified with permission) – has improved educator confidence in identifying children with delayed communication and knowing what to do when a communication difficulty was suspected ([name] et al., in preparation). Furthermore, educators reported increased confidence using a wide range of interaction skills to support communication development.

The training has been adapted from a well-established training program developed by the Hanan Centre® in Canada. However, evaluations of the standard training (i.e., Flowers et al., 2007; Giromalletto et al., 2003; McDonald et al., 2015) and subsequent adaptations by other research teams around the world (i.e., Cabell et al., 2011; Piasta et al., 2012) have failed to consider the impact of this type of training on multilingual educators and the multilingual/multicultural children in their care. No previous investigations have considered the impact of this training on the communication behaviours of a diverse range of language speakers in their educator and/or child populations. The current investigation, therefore, serves two purposes: (1) to establish whether the locally adapted Training has a direct impact on educator and child communication behaviours during periods when educators are, and are not, engaging in the Training, and (2) to establish whether any changes in communication

behaviours are consistent in English and any additional language/s shared by educators and the children in their care.

Educators have access to a large number of children. They are therefore well-positioned to provide high quality communication opportunities to children of all language abilities. As a result, the potential magnitude of the impact they can have on children in ECECs is far greater than any single speech pathologist could provide through traditional methods. Furthermore, the significant and far-reaching impacts of early language intervention and prevention in the early years are well-established. The results of the current study will inform future ongoing implementation of this training and/or guidance for early childhood educators and education centres in the local area, with a view to improve the communication environments for all children in Western Sydney.

The Training

In 2019, the Speech Pathology team within the Child and Family, Integrated and Community Health service of WSLHD began providing training to early childhood educators in the local area. The training is based on the Learning Language and Loving It™ training developed by the Hanen Centre®. Learning Language and Loving It™ is a valid, evidence-based professional development program which addresses the pivotal role of the early childhood educator in facilitating children's social, language and literacy skills. This program uses the most current research in the areas of childhood education, language development and adult learning to promote developmentally appropriate interactions which are associated with positive language and literacy outcomes for the young children who attend child care. The Training that will be provided as a part of the current study has been adapted locally, through discussion with a local reference group of educators, directors, local council representatives and service providers to suit the needs of the local community. The subsequent adaptation has been approved by The Hanen Centre® and is the first adaptation to be trialed with a distinctly culturally and linguistically diverse population. The Training includes educator attendance at five workshop sessions with a group of their peers and three 1-on-1 coaching sessions in their early childhood education centre workplace with a speech pathologist from WSLHD. This is a truncated version of the full Learning Language and Loving It™ training which involves eight workshop sessions and six video feedback sessions. The modifications were made to make implementation more feasible given educator work commitments, availability for out-of-hours training, and speech pathology resources.

The aim of the Training is to teach early childhood educators responsive interaction strategies that are known to promote the social and communication development of young children and determine the impact of these strategies on children's language production. These strategies include: (1) Child-oriented strategies to support children to engage in conversation and initiate new interactions, (2) Interaction-promoting strategies that can facilitate the extension of language opportunities during individual and group interactions, and (3) Language modelling strategies that expand on children's current communication abilities to increase the complexity of their communication in familiar and unfamiliar communication contexts.

If restrictions and policies surrounding arising from the COVID-19 pandemic impact the planning and implementation of the training, the training may be delivered online. The Hanen Centre® has created an online version of the program which is equivalent in content, structure and duration.

5. STUDY OBJECTIVES

5.1 RESEARCH QUESTIONS

This study will include two primary research questions relative to each participant group. Secondary research questions have also been identified for each participant group. Primary and secondary research questions are listed below.

5.1.1 Was the magnitude of change in children’s mean length of utterance greater during a period of educator training when compared to a control period with no training (Stage 1 comparison)?

5.1.1.1 Was the magnitude of change in children’s mean length of utterance during a training period comparable to a post-training follow up period (Stage 2 comparison)?

5.1.2 Was the magnitude of change in overall educator interaction skills observed greater during a period of educator training when compared to a control period with no training (Stage 1 comparison)?

5.1.2.1 Was the magnitude of change in overall educator interaction skills observed during a training period comparable to a post-training follow up period (Stage 2 comparison)?

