5.6.1 Research time frame

The timeframe for the current study will be 20 months from the time of recruitment until the end of the final stage of data collection. Data will be collected at five time points for all participant dyads: (1) recruitment and screening of participants (Time 1), (2) before Stage 1 Training (Time 2), (3) after Stage 1 Training (Time 3), (4) before Stage 2 Training (Time 4), and (5) after Stage 2 Training (Time 5) (see Table 1). Both training stages will be 8-weeks in length and there will be a five-week period between Stage 1 and Stage 2 within which Time 3 and Time 4 data will be collected from all dyads. Analysis and dissemination will continue for approximately 12 months from the completion of data collection.

Table 1. Research Time Frame

Study Time Frame	2021						2022
	Apr- Jun	Jul	Jul- Sep	Sep	Oct- Dec	Dec	Jan- Dec
Time 1: Recruitment and screening	2 mths						
Time 2: Data collection before Stage 1		1-2 wks					
Stage 1: Training implemented with Group A			8-wks				
Time 3: Data collection after Stage 1				1-2 wks			
Time 4: Data collection before Stage 2				1-2 wks			
Stage 2: Training implemented with Group B					8-wks		
Time 5: Data collection after stage 2						1-2 wks	
Data analysis and dissemination							12 mths

Time 1 will include the collection of demographic information about Educator and Child participants and confirmation of child eligibility to participate in the research. Times 2-5 are for the purpose of collecting outcome measure data. Difference scores on the primary and secondary outcome measures will be calculated between Time 2 and Time 3 (Difference Score 1, Stage 1) and Time 4 and Time 5 (Difference Score 2, Stage 2). Data for the current study will be collected from video recordings of adult-child interactions completed at Times 2, 3, 4 and 5. Data will include the extent to which the educator demonstrates interaction strategies and the language productivity and complexity demonstrated by the child in each dyad (see Table 2 for the data collection schedule). The inclusion of post-training evaluation of interactions at Time 4 and 5 is to determine the maintenance of interaction strategies demonstrated by Educators in Group A as well as any change in children’s language during a period of no active Educator training.

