8.2 STATISTICAL METHODS TO BE UNDERTAKEN

All questionnaire data will be collected via Microsoft Teams and exported in raw format for processing in R or SPSS. Demographic information (including age, languages spoken, language proficiency, educator level of education, educator years of experience, and child communication measures [ASQ and PLS]) will be described for all dyad participants. Two multiple linear regression analyses will be conducted to address the primary aim (Stage 1 contrast) and our secondary aim (Stage 2 contrast). The outcome (dependent variable) for both analyses will be children's mean length of utterance Difference Score across each Stage. Independent variables will be Group allocation (A or B) and cluster (ECEC). This analysis plan will allow for the primary investigation to be conducted on data collected in Stage 1. This primary analysis will investigate the impact of group allocation (Training [Group A]; Control [Group B]) and cluster (Educator Centre) on children's language output (Mean Length of Utterance). The secondary investigation will be conducted on data collected in Stage 2. This secondary analysis will investigate the impact of group allocation (No-training follow-up [Group A]; Training [Group B]) and cluster (Educator centre) on children's language output.

Intention-to-treat analysis will be completed in the event of educator drop-out from the training. If appropriate, per-protocol analysis will be completed to investigate the primary and secondary outcomes.

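### The Stage 2 questions ask whether changes are comparable, but the planned contrast cannot establish comparability and cannot assess maintenance of educator skills in Group A

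*Protocol*

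**What the plan says.** Section 5.1 poses two Stage 2 questions, one on child MLU (5.1.1.1) and one on overall educator interaction skills (5.1.2.1). Each asks whether the change was "during a training period comparable to a post-training follow up period (Stage 2 comparison").

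Section 8.2 plans two linear regressions, one per stage. The outcome of both is the child's "mean length of utterance Difference Score across each Stage". On the predictors it says: "Independent variables will be Group allocation (A or B) and cluster (ECEC"). The Stage 2 analysis examines the effect of "group allocation (No-training follow-up [Group A]; Training [Group B"]). No margin or other criterion for comparability is given, and no regression is stated for the educator composite.

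Section 5.6.1 defines the Stage 2 score as the change between "Time 4 and Time 5 (Difference Score 2, Stage 2"). It also says that recording after training at Times 4 and 5 "is to determine the maintenance of interaction strategies demonstrated by Educators in Group A", and additionally serves to observe change in children's language while no training is under way.

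The only sample size calculation, in section 8.1, concerns the difference that can be detected with 80% power.

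**The concern.** A between-group regression estimates a difference. It can support a claim that two changes are alike only if a margin says how alike is enough and the confidence interval falls inside it. Section 5.1 asks for likeness and the protocol supplies no margin. In a study of this size, a non-significant Stage 2 result would be common even when the two changes differ materially.

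The second problem is the aim of the follow-up. Whether Group A educators keep what they learned is a question about Group A's level after training, measured against its level when training ended (Time 3). The Stage 2 contrast instead sets Group A's Time 4 to Time 5 change against Group B's gain while it is being trained. Those two quantities should agree when training has no effect and disagree when training works and skills are held, so the contrast does not track maintenance.

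At stake is whether the two secondary questions, and the reason given for following Group A to Time 5, can be answered by the plan as written.

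**Working it through.** **Inputs (section 8.1):** 12 dyads per group, as 6 centres of 2; SD of change 0.3; ICC 0.1; alpha 0.05, taken as two-sided; power 0.8; stated detectable difference 0.358; previously observed difference 0.4. Section 8.1 does not say which outcome the SD and the 0.4 belong to. They are applied here to MLU, as an assumption.

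**1. Reproducing the protocol's figure.**
- Design effect = 1 + (2 − 1) × 0.1 = 1.1.
- SE = 0.3 × √(1.1 × 2/12) = 0.1285.
- Detectable difference = (1.960 + 0.842) × 0.1285 = 0.360, against 0.358 stated.

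The figure is reproduced closely by a normal approximation for a test of difference. With 10 df (12 centres − 2) it would be 0.399. Both bases are carried below, because the protocol's figure fits the first and the number of centres argues for the second.

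**2. Precision of the Stage 2 contrast.**
- Normal: 1.960 × 0.1285 = 0.25.
- 10 df: 2.228 × 0.1285 = 0.29.

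**3. Probability of a non-significant result, by true difference.** The normal formula is 1 − [Φ(d/SE − 1.960) + Φ(−d/SE − 1.960)]; the other column uses the noncentral t with 10 df.

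| True difference | Normal | 10 df |
|---|---|---|
| 0 | 95% | 95% |
| 0.2 | 66% | 71% |
| 0.3 | 35% | 44% |
| 0.4 | 12% | 20% |

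A difference of half the 0.4 benchmark is missed about two times in three. Non-significance therefore says little about comparability.

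**4. What a margin would need.** The protocol gives none, so 0.2, 0.3 and 0.4 are assumed. With a true difference of 0, the power for the interval to lie within ±M is 2Φ(M/SE − z) − 1 (or 0 if negative), on the normal basis with SE taken as known.

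| Margin | 90% interval (z = 1.645) | 95% interval (z = 1.960) |
|---|---|---|
| 0.2 | 0% | 0% |
| 0.3 | 51% | 29% |
| 0.4 | 86% | 75% |

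The margin that gives 80% power is (z + 1.282) × 0.1285, which is 0.38 for the 90% interval and 0.42 for the 95% interval. Only a margin about as large as the whole expected effect is workable.

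**5. Maintenance of educator strategies.** Write the Group A Time 4 to Time 5 change as a and the Group B change as b. Full maintenance means a ≈ 0.
- Training works: b > 0, so the groups differ although skills were kept.
- Training does nothing: b ≈ 0, so the groups match although there was nothing to keep.

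This is an argument about the contrast and needs no SD. To show its strength at the section 8.1 inputs only: with b − a = 0.4 the difference test is significant with probability 88% (normal) or 80% (10 df), and with b − a = 0 it is non-significant with probability 95%. These percentages should not be carried to the educator composite, a sum of eight averages for which no SD is identified.

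**6. The gap between stages.** Difference Score 1 is T3 − T2 and Difference Score 2 is T5 − T4. For Group A, T5 − T3 = (T4 − T3) + Difference Score 2. The term T4 − T3 is in neither score, so any loss soon after training ends is not counted.

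**The case against.** Several stronger readings are tempting, and the protocol does not support them.

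- *Both questions are answered by this regression.* Section 8.2 names MLU as the outcome of both models. Question 5.1.2.1 has a defined contrast and difference score but no stated test.
- *A non-significant result will be declared comparable.* The protocol nowhere says so. A statistical analysis plan, not available here, could add a margin or an interpretation rule. What stands is that the protocol offers no criterion, and that the sample suits only a very wide margin.
- *The reversed answer applies to child MLU.* The maintenance aim concerns educators: "to determine the maintenance of interaction strategies demonstrated by Educators in Group A". Typically developing children aged 24 to 42 months are expected to gain language without training, so zero change is not their benchmark. For MLU, 5.1.1.1 can fairly be read as asking whether the rate of gain continues, and a finding of unequal change could then be a correct answer.
- *Section 4.2 contradicts section 5.1.* It says: "We hypothesise that there will be a greater magnitude of communication behaviour change during a period of training". Yet the sentence before it asks whether change is commensurate in the two periods. The protocol seems to use such words loosely for how the periods compare. That is imprecise wording, not a demonstrated contradiction.
- *Nothing collected in Stage 2 can speak to maintenance.* Time 3, 4 and 5 recordings are planned for all dyads, so levels can be compared. The fair statement is that the Stage 2 contrast does not do this and no other maintenance analysis is stated. Times 3 and 4 also both fall within a five-week gap, so the uncounted interval is short.

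A simple Time 3 to Time 5 change has weaknesses of its own. It is uncontrolled, and sections 6.1.2 and 7.4 allow participants to be replaced between stages. Both limits are respected in the fix.

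**Conclusion.** The point holds and should be corrected, although it concerns secondary questions. As written, the Stage 2 contrast cannot establish comparability of MLU change. There is no margin, the interval is about ±0.25 to ±0.29, and a true difference of 0.2 goes undetected in 66% to 71% of trials. For the educator composite the same contrast is posed without a model. It would not measure maintenance in Group A, because agreement with Group B is expected when training fails and disagreement when it works and skills are kept.

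The numbers rest on SD 0.3 and ICC 0.1 applying to MLU, full recruitment of 12 dyads per group, and centre handled through the design effect as in section 8.1. The range reflects normal against 10 df calculations. The maintenance argument rests on none of these. Its first half (disagreement despite full maintenance) assumes that training has an effect, which is the protocol's own hypothesis. A reader might infer that the protocol intends to claim comparability from a non-significant p-value; it does not say that, and the finding does not depend on it.

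**What to change.** 1. Reword 5.1.1.1 and 5.1.2.1 as estimation: the Stage 2 difference in change (Group B minus Group A) with a 95% confidence interval, allowing for centre. State that a non-significant p-value supports no claim of comparability, and name the model for the educator composite. If *comparable* is kept, require the interval to lie within a margin fixed and justified before analysis, noting that at the section 8.1 inputs only a margin near 0.4 would be adequately powered.
2. Assess educator maintenance separately: the Group A change in the composite from Time 3 to Time 4 and to Time 5, and from Time 2, each with a 95% interval. Restrict each estimate to educators recorded at both times, and flag dyads whose child was replaced between stages.
3. Do not interpret the Group A Time 3 to Time 5 change in MLU as maintenance. It is uncontrolled and confounded with normal language growth.

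Cost: new wording for two secondary questions, a short addition to section 8.2 and slight extra analysis. The recordings are already scheduled, although replacements may reduce the number of educators with both time points. The price is more modest wording of what Stage 2 can show.
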